3.2 Rationale for Study Design

Ocrelizumab and rituximab are among the most effective disease modifying therapies studied to date. Also, their safety profile to date (in terms of serious adverse events) is better than the other highly effective therapies including natalizumab, fingolimod, alemtuzumab, daclizumab and dimethyl fumarate. Several centers including the RMMSC and the Swedish Coalition of MS Clinics have large MS populations on rituximab, some for more than 6 years. However, rituximab does not have a patient assistance program, will remain off label for MS and will have significant uncertainty about access for the seeable future. Also, Ocrelizumab has been positioned to possibly be superior to rituximab in terms of IRRs, ADA and efficiency of B cell depletion. Although, these statements have not been proved, they will be influential to some MS patients, rituximab prescribers and third party payers. Thus a significant amount of

switching from rituximab to ocrelizumab is likely to occur. We know of no data describing the consequence of such switching in terms of IRRs, formation of ADAs and efficiency of B cell depletion. The proposed study has good power to address these 3 issues. It is not powered to look at any efficacy outcomes and none are included. We will monitor for safety per standard operating procedures for our study team.

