Earlier concepts of MS disease pathology have suggested that pathogenic T cells are sufficient for the full expression of MS. However, it is now evident that full autoimmune B cells and humoral immune mechanisms also play key roles.⁵ Ocrelizumab is a humanized monoclonal antibody that targets CD20 and selectively depleted CD-20 expressing B cells. CD20 is a B cell surface molecule that is expressed on pre B cells and mature B cells, but not expressed earlier in the development of B cells or on mature plasma cells. In all three ocrelizumab studies (with relapsing and progressive populations), treatment with 600 mg of ocrelizumab led to rapid and complete depletion of circulating CD19⁺ B cells within 14 days post treatment.⁴ B cell depletion was sustained throughout treatment period. The median time to repletion of B cells was 72 weeks (range 27-175 weeks). We hypothesize that in switching rituximab treated patients to ocrelizumab, the proportion of patients with B cell depletion (CD19⁺ and CD20⁺ ≤ 1%) 6 months after the first and third infusion of ocrelizumab will be the same as the baseline assessment which will be 6 months after the last dose of rituximab and similar to findings in OPERA I and II.

Immunogenicity results from the OPERA I and II trials examined the number of patients who had treatment induced anti-drug antibodies (ADA) to ocrelizumab.⁴ Of the 807 patients who received ocrelizumab and had an ADA assay from a post baseline sample during the controlled treatment period, 3 patients (0.4%) showed treatment induced ADA to ocrelizumab. Of these, 1 patient tested positive for neutralizing antibodies (NAB) to ocrelizumab. During the open label extension phase, the prevalence of ADA continued to remain low with post baseline incidence of 1.9% (2/103 with treatment induced ADA). Currently there is little evidence examining the prevalence of treatment induced ADAs to both rituximab and ocrelizumab in patients that switch from the former to the latter in comparison to continuing rituximab patients. Therefore, we will perform assays to detect ADAs to both rituximab and ocrelizumab in all patients switching from rituximab to ocrelizumab at Day 1, 6 months and between 12 and 18 months on ocrelizumab.

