Finally, IRRs have been hypothesized to be a reaction by autoantibodies to the treatment drug or possibly from the release of cytokines from CD20 expressing cells as they are destroyed by ocrelizumab causing a “cytokine storm”. Understanding this process may lead to mechanisms that may aid in ameliorating these infusion reactions. If they are associated with ADA, then it might be possible to predictively premedicate these patients only. Alternatively, if they are associated with cytokine release, it may be possible to eliminate premedication in patients who are already CD20⁺ cell depleted in subsequent infusions. Therefore, we will assay the profile of certain cytokines in the serum 4 hours after start of ocrelizumab infusion.

Since ocrelizumab has entered the market, third party payers within and outside the US have required that the FDA or EMA approved versions of anti-CD20 monoclonal antibodies be used in the treatment of MS, namely ocrelizumab. Currently, we estimate several thousand MS patients in the US and Sweden are taking rituximab currently. Thus, it will be important to demonstrate that switching from a chimeric anti-CD20 to a more fully humanized anti-CD20 does not lead to unexpected infusion reactions and does not increase the probability of development of anti-drug antibodies.

The Rocky Mountain MS Center (RMMSC) at the University of Colorado Anschutz Medical Campus prescribed rituximab infusions for 533 MS patients in the last 12 months, of which 323 patients received their infusion at the University of Colorado Hospital's Outpatient Infusion Center between September, 2015-March, 2016. The RMMSC is one of the few sites nationwide with large numbers of MS patients treated with rituximab. On March 28, 2017, Ocrevus (ocrelizumab) was approved by the FDA for the treatment of primary progressive and relapsing multiple sclerosis. With the approval of ocrelizumab, current rituximab users are being counselled by their MS providers at RMMSC to consider switching to ocrelizumab if it is the only anti-CD20 MAB covered by their insurance.

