2.2 Secondary Objectives

Secondary Objective: Our secondary objective is to assess the impact of switching from rituximab to ocrelizumab (**only in the switching group**) on the incidence and prevalence of anti-drug antibodies to ocrelizumab. The presence of anti-drug binding antibodies will be assessed prior to the first and third ocrelizumab infusion and six to twelve months after the last ocrelizumab infusion. The serum drawn before the first infusion of ocrelizumab will be the baseline comparator since these patients will only have been exposed to at least two rituximab infusions over 6 months with no prior exposure to ocrelizumab. This means we will have 100 serum samples prior to ocrelizumab exposure and 200 after ocrelizumab exposure. These assays will be performed by PPD Bio A

Laboratories (in Richmond, VA) who will assess the anti-drug antibodies to ocrelizumab”, and “QPS (Netherlands) who will assess the anti-drug antibodies to rituximab as a single batch once all samples have been collected and cryopreserved.

Other secondary objectives that will be assessed in **the switching group** only include the following:

- a. We will assess the percent of ocrelizumab treated patients that exhibit early recovery of CD19+ and/or CD20+B cells (>1%) prior to each ocrelizumab infusion and at month 12 or 18 which is 12 or 18 months following the first infusion of ocrelizumab. We will compare this to the percent of patients with evidence of early recovery from rituximab as assessed by the baseline B cell panel. Our test will also identify CD19 antigen expression to confirm depletion since presence of anti-CD 20 MAB in patients blood may confound the CD-20 expression assay.
- b. We will assess cytokines to evaluate for possible contribution of a cytokine storm to infusion reactions. Cytokines will be assessed using the MesoScale platform. These blood samples will be collected before the start of each ocrelizumab infusion and following infusion completion. Blood samples will also be collected during a moderate or serious IRR.
- c. We will describe all adverse events and serious adverse events in addition to IRRs (for example infections) as described in the investigator’s brochure.

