4.9.4 Safety Analysis

The default analysis will be available case for all eligible participants on an intent to treat basis. Alpha = 0.05 for all tests. As in the OPERA I and II randomized clinical trials, the primary and secondary end points will be descriptively presented. Frequencies and percentages for the severity of IRR grades (Grades 0-5) will be presented for both study groups following each infusion time point and overall between groups. 95% confidence intervals for the proportions will be calculated. Differences in the distribution of IRR severity grades between independent samples (i.e. comparison between groups at a common time point) will be tested with the chi-square or Fisher's exact association test, and additionally with ordinal or multinomial logistic regression. If sample sizes are small among some levels of IRR severity grades, they may be collapsed or dichotomized (i.e. Grade 3 or higher, any reaction or no reaction, severe reaction or none as examples) and methods described for binary outcomes under secondary endpoints will be utilized. Dichotomization may be used to make analysis and presentation of results more manageable as well.

The primary endpoint will be the proportion of whether any IRR occurred (yes or no) per infusion cycle per patient in each study group. The secondary endpoints include the proportion per infusion per patient of severe infusion reaction (grade 3 or greater), the proportion of infusion reactions and severe infusion reaction per patient across all infusions, the proportion patients with anti-drug antibodies, and the proportion of patients with depleted B cells. The primary outcome, binary occurrence of IRR per infusion per patient, could be analyzed with logistic or relative risk models, with GEE (generalized estimating equations) and/or GLMM

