4.9.6 Determination of Sample Size

The sample size will be a convenience sample. It is anticipated a minimum of 100 patients will qualify for each cohort (200 total) resulting in studying 300 infusions with ocrelizumab and 200 infusions with rituximab. This is an observational study not designed to demonstrate superiority of ocrelizumab over rituximab in efficacy but instead indicate the magnitude of the relative tolerability and immunogenicity. The primary endpoint is the difference in the percentage of IRRs between the two study groups. In addition, both study groups will include treatment experienced patients on rituximab who have experienced a minimum of two infusions and either continue to stay on rituximab or switch to ocrelizumab.

To estimate study power with the proposed sample size of 100 infusions in each group, we conducted a chart review of 50 patients at the Rocky Mountain MS Center who are currently taking rituximab and examined their IRRs using the proposed IRR grading scale (see section 3.3.1) from Grade 0-5. The number and severity of IRRs were captured following their third rituximab infusion. The highest grade of an IRR that occurred during the infusion was recorded. Our pilot data revealed that following the third rituximab infusion, 14.3% of patients had an IRR of which 85.71% were Grade 0, 12.24% were grade 2 and 2.05% were Grade 3. Hauser et al., found that following the second infusion of rituximab in patients, the majority of whom (60%) were not taking a DMT for 6 months prior to initiating rituximab only 20.3% experienced in an IRR.³

Using IRR estimates from our pilot data and establishing a clinically meaningful difference of 20% increase in IRRs, we conducted the following power analysis for a sample of 95 patients (assuming a 5% attrition rate after recruiting 100 patients in each study group). An IRR proportion for ocrelizumab users at 34.3% compared with 14.3% for rituximab (obtained from our pilot data) for a two sided (alpha = 0.05) two sample proportion test for the null hypothesis of no difference between rituximab and ocrelizumab in proportion of IRRs would result in 90% power for 95 patients per group.

In response to the FDA IND letter, “the power analysis in Section 4.9.6 of the protocol appears to compare the infusion-related reaction (IRR) rate at the third rituximab infusion (14.3%) to that of the first infusion of OCR (34.3%). Because

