the incidence of an IRR for most monoclonal antibodies is highest with the first infusion and declines with subsequent infusions, we recommend that you revise your sample size and power calculations using the IRR incidence for a comparable number of infusions; for example, the first, second, or third infusion”:

Our response is that neither the switching and comparison groups are receiving their very first infusion of any anti-CD 20 monoclonal antibody (rituximab or ocrelizumab) following enrollment in the study. Both study groups have received a minimum of at least two infusions of rituximab prior to enrollment in the study. The first study related infusion for ocrelizumab in the switching group represents (at minimum) their third infusion for an anti-CD monoclonal antibody which will be compared to their third standard of care infusion for rituximab (at minimum) following study enrollment. As a result, we believe both groups represent those patients who have experienced at least three infusions of an anti-CD monoclonal antibody agent. Thereby our power calculations were based on the IRRs observed following the third infusion of rituximab in our pilot sample (at 14.3%) and using a clinically meaningful difference of 20% increase in IRRs for the ocrelizumab group (34.3%) to provide 90% power for 95 patients per study group (assuming a 5% attrition rate after recruiting 100 patients in each study group).

As there is only one primary outcome to power the study on, there is no need to reduce the alpha level of the univariate test as part of multiple testing adjustment. Adjustment for interim analysis is not an issue as there are no early stopping rules.

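### Section 3.2 claims good power for three issues, but power is calculated only for IRRs; for ADA to ocrelizumab the claim fails for rises within the range the protocol reports, and for rituximab ADA and B cells it is unsupported

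*Combined protocol and SAP*

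**What the plan says.** Section 3.2 notes that no data exist on what switching does to IRRs, ADA formation and the efficiency of B-cell depletion, and then states "The proposed study has good power to address these 3 issues".

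The only power calculation is in Section 4.9.6. It assumes "An IRR proportion for ocrelizumab users at 34.3% compared with 14.3% for rituximab", uses a "two sided (alpha = 0.05) two sample proportion test", and reports 90% power with 95 patients per group. The same section argues against adjusting alpha with the words "As there is only one primary outcome to power the study on".

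ADA is a secondary outcome measured in the switching group only (Sections 2.2 and 3.3.2). On sample numbers, Section 2.2 says "This means we will have 100 serum samples prior to ocrelizumab exposure and 200 after ocrelizumab exposure". There are two comparators: each patient's serum from before the first ocrelizumab infusion (Section 2.2) and the OPERA trials (Section 3.1). For OPERA the Introduction reports that, of 807 patients, "3 patients (0.4%) showed treatment induced ADA to ocrelizumab", and gives 2/103 (1.9%) for the open-label extension. It also says it will be important to show that switching "does not increase the probability of development of anti-drug antibodies".

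For B cells, the Introduction hypothesises that the depleted proportion will match baseline and resemble OPERA. It gives neither an expected proportion nor a margin.

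**The concern.** The protocol claims power for three outcomes and derives it for one. ADA to ocrelizumab is rare in the only data cited, is assessed in one group, and has about 100 patients behind it. The 200 samples taken after exposure are repeat samples from those patients. They do not double the sample size, because Section 3.3.2 counts patients.

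What is at stake is how the most likely result will be read. If the true rate equals 3/807, there will be zero or one positive patient with probability 95%. Next to a statement of good power and the Introduction's wish to show no increase, that result invites the conclusion that switching does not raise ADA. The data would not exclude rises several times larger than either OPERA rate suggests.

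**Working it through.** **1. The plan's own figure (IRR, Section 4.9.6).** Inputs: p1 = 0.143, p2 = 0.343, n = 95 per group, two-sided alpha 0.05. The mean proportion is 0.243.

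z = [0.20·√95 − 1.96·√(2·0.243·0.757)] / √(0.143·0.857 + 0.343·0.657) = (1.949 − 1.189)/0.590 = 1.29, so power = Φ(1.29) = 90.1%. The stated 90% reproduces.

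**2. Inputs for ADA to ocrelizumab.** n = 100 (Section 2.2), or 95 after the 5% attrition in Section 4.9.6. OPERA rates: 3/807 = 0.37% and 2/103 = 1.94% (Introduction). Test level: "Alpha = 0.05 for all tests" (Section 4.9.4), taken as two-sided, so 0.025 in the upper tail.

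**3. Against OPERA 0.37% taken as fixed (exact binomial, n = 100).**
- Expected positives: 100 × 0.0037 = 0.37. P(no positives) = (1 − 3/807)^100 = 0.689.
- P(X ≥ 2) = 0.054 and P(X ≥ 3) = 0.0064, so at least 3 positives are needed.
- Power = P(X ≥ 3 | n, p):

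| True rate | Power, n = 100 | Power, n = 95 |
|---|---|---|
| 0.74% (doubling) | 4% | 3% |
| 1.94% (2/103) | 31% | 28% |
| 3% | 58% | 55% |
| 4% | 77% | 74% |
| 5% | 88% | 86% |

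- 80% power is reached at a true rate of 4.2% (n = 100) or 4.5% (n = 95).
- Treating 3/807 as itself a sample (Fisher exact, n = 100) gives 6% for a doubling, 35% at 1.94%, 61% at 3% and 89% at 5%. The picture is the same.

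**4. Against the patients' own baseline (exact two-sided McNemar, no reversions from positive to negative).** With m new positives and none in the other direction, p = 2 × 0.5^m. Five give 0.063 and six give 0.031, so six are needed. Power = P(X ≥ 6 | 100, p): about 1% at 1.94%, 38% at 5%, 82% at 8%. 80% power needs about 7.8% new positives.

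**5. What a low count would exclude (exact 95% upper limits).**
- 0/100: 1 − 0.025^(1/100) = 3.6%. This is 3.62/0.37 ≈ 10 times the controlled-period rate, or 3.62/1.94 ≈ 1.9 times the open-label rate.
- 0/95: 3.8%.
- 1/100: 5.4%, about 15 times 0.37% or 2.8 times 1.94%.

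**6. Size needed for a rise to 1.94%.** Detecting it against a fixed 0.37% takes about 284 patients for 80% power. Excluding it takes zero positives in at least 189.

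**7. ADA to rituximab and B-cell depletion.** The documents give no rituximab-ADA rate, no expected depleted proportion and no rate of change from baseline. Power cannot be computed from them.

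**The case against.** The best defence is that these are secondary outcomes, which need no power, and that the statistical section never relies on the sentence in Section 3.2. Section 4.9.4 says endpoints will be presented descriptively and allows exact intervals when counts are small. Section 4.9.6 describes the purpose as indicating the size of relative tolerability and immunogenicity, and confines power to one primary outcome. The Introduction's wish to show no increase is motivation; the plan has no equivalence margin and no rule for declaring no increase. All of that stands, and it keeps this a matter of wording. It does not withdraw the claim in Section 3.2, which still conflicts with Section 4.9.6.

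Two further points also stand. First, the tenfold figure depends on the benchmark: against the open-label rate, the upper limit for 0/100 is less than twofold. Both ratios belong in any account. Second, a reader might infer that the study cannot detect any rise in ADA. The figures do not support that: power against OPERA is 88% if the true rate is 5%. The documents give no expected rate after switching, so they cannot settle whether 5% is implausible.

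The within-patient comparator does not rescue the claim. It needs six new positives rather than three.

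**Conclusion.** The claim of good power is supported for IRRs only. For ADA to ocrelizumab it is wrong for rises within the range the protocol itself reports (0.37% to 1.94%): power at the top of that range is 31% against OPERA and about 1% against baseline. Good power against OPERA begins at a true rate a little above 4%.

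These figures assume one result per patient, 95 to 100 evaluable patients, two-sided alpha 0.05 and, for the paired test, no reversions. Reversions would lower paired power further.

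A reader might go on to conclude that the study is also underpowered for B-cell depletion or for ADA to rituximab. The documents do not support that. Without a rate or margin, the answer depends wholly on the values assumed, so the claim there is unsupported, not shown false. The B-cell hypothesis is one of sameness, however, and without a margin a non-significant test would not establish it.

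The primary analysis and its sample size are unaffected.

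**What to change.** Replace the power sentence in Section 3.2 with wording such as:

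> The study is powered only for the IRR comparison. ADA and B-cell results are estimates with exact 95% confidence intervals; if no patient develops ADA to ocrelizumab, rates above about 3.6% (n = 100) to 3.8% (n = 95) are excluded and smaller increases are not.

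In Section 4.9.4, say that ADA conclusions will be stated through the upper confidence limit, set beside both OPERA rates, and not as a finding of no increase. Give no power figure for B cells or for ADA to rituximab, since the documents offer nothing to base one on.

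The cost is protocol wording only: no extra patients, samples or assays, and no change to any endpoint or test. The stated claim becomes less favourable.

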3.3 Outcome Measures

3.3.1. Primary Outcome Measure

Primary endpoint:

- a. Primary endpoint: The primary end point will be proportion of infusions with ≥ 1 IRR between the switching and comparator groups.
- b. Secondary IRR assessments:
 - a. We will also report the difference in the total number of IRRs after each infusion of ocrelizumab in the switching group compared to similar rituximab infusions in the comparator group.
 - b. The difference in proportion of patients with ≥ 1 IRR across any of their infusions between the switching and comparator groups
 - c. We will also compare the proportion of patients with an IRR following day 1 infusion versus the proportion of patients with an IRR at day 15 and month 6 infusions of ocrelizumab in the switching group.
 - d. The severity of IRRs will be assessed following each infusion of ocrelizumab in the switching and comparator group using the National Cancer Institute's Common Terminology for Adverse Events Scale.⁶ The frequency of each severity grade of IRR will be compared in a similar fashion.

Nursing staff at the University of Colorado's Outpatient Infusion Center will be responsible for classifying the severity of an IRR for each patient at the end of every ocrelizumab and rituximab infusion using the scale below. Nursing staff will be asked to record the highest grade of an IRR that they observed or intervened upon for each patient after completion of their infusion.

Severity of IRR:

Grade 0: No infusion reaction

Grade 1: Mild reaction (transient flushing or rash drug fever < 38 degrees C); infusion interruption not indicated; intervention not indicated

Grade 2: Requires therapy or infusion interruption but responds promptly to symptomatic treatment (e.g., antihistamines, NSAIDs, narcotics); prophylactic medications indicated for 24 hours.

Grade 3: Prolonged (i.e., not rapidly responsive to symptomatic medication and/or brief interruption of infusion); recurrence of symptoms following initial improvement; hospitalization indicated for other clinical sequelae (e.g., renal impairment, pulmonary infiltrates)

Grade 4: Life threatening consequences; urgent intervention indicated.

Grade 5: Death

